- Specific Aim 1:** to compare the change in myopia between single vision contact lens wearers and soft bifocal contact lens wearers to test the hypothesis that soft bifocal contact lenses slow myopia progression in a dose-dependent manner in children,
- Specific Aim 2:** to determine whether peripheral defocus created by soft bifocal contact lenses is associated with myopia progression to test the hypothesis that peripheral myopic defocus slows myopia progression in children, and
- Specific Aim 3:** to determine whether changes in ocular shape differ between children wearing single vision and soft bifocal contact lenses to test the hypothesis that peripheral myopic defocus globally slows eye growth.

Chapter 4: Study Design

This is a multi-center, randomized clinical trial. Subjects will be randomly assigned to wear single vision contact lenses, soft bifocal contact lenses with a +1.50 D add, or soft bifocal contact lenses with a +2.50 D add for at least three years. Figure 4-1 illustrates the study schedule.

Figure 4-1: Flowchart illustrating the visit schedule and randomization.

Chapter 5: Sample Size

All sample size calculations were performed using PASS 2005 software using $\alpha = 0.05$ and $\beta = 0.10$ (power = 80%). Estimates of sample size were computed for each specific aim.

Specific Aim 1: to compare the change in myopia between single vision contact lens wearers and soft bifocal contact lens wearers to test the hypothesis that soft bifocal contact lenses slow myopia progression in a dose-dependent manner in children

Aim 1 is designed to compare myopia progression between two soft bifocal adds and single vision contact lens wearers using the mean value of the cycloplegic spherical equivalent (sphere + $\frac{1}{2}$ cylinder) as measured at one, two, and three years. These comparisons will be made using the common estimate of error obtained from a three group x three time point repeated measures analysis of covariance (ANCOVA), with the baseline spherical equivalent used as a covariate. To increase the efficiency of the F-tests performed as part of the ANCOVA, the total sample size will be equally allocated between the soft bifocal and single vision contact lens groups.

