Sample size calculations are driven, in part, by the desired difference in spherical equivalent change between the three groups. This difference needs to be of a magnitude that is considered clinically relevant. Sample sizes are based upon the percent reduction in myopia progression between the two soft bifocal contact lens groups and the single vision contact lens group. Data used in the calculations are taken from the single vision contact lens group of the ACHIEVE Study, where the mean (\pm SD) myopia progression was $-1.29 \text{ D} \pm 0.71$ over three years (Walline et al., 2008). If we want to detect a 50% treatment effect (reducing the amount of myopia progression by roughly 0.65 D in the +2.50 D add group) and we estimate that the mean treatment effect for the +1.50 D add group is halfway between the single vision contact lenses and the +2.50 D add group (i.e., reducing myopia progression by 0.30 D in the second add), then the sample size required at 80% power is 24 per treatment group. Estimating the effect of the +1.25 D add group to be halfway between the two groups results in the largest sample size possible (a conservative estimate). Should we find that both adds have a similar effect, we will be more than adequately powered. If we look at a reduction of 0.50 D (a treatment effect of 40% in the highest add group), then the sample size is 40 per treatment group at 80% power. A 30% treatment effect (a reduction of about 0.40 D in the amount of myopia progression in the +2.50 D add group) yields a sample size of 62 subjects per treatment group.

Specific Aim 2: to determine whether peripheral defocus created by soft bifocal contact lenses is associated with myopia progression to test the hypothesis that peripheral myopic defocus slows myopia progression in children

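### If Aim 1's common error term is pooled over years, a three-year arm comparison gets too small a standard error whenever the spread of progression grows with time

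*Combined protocol and SAP*

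**What the plan says.** Chapter 5 (Sample Size, Specific Aim 1) compares the two bifocal adds with single vision on cycloplegic spherical equivalent "as measured at one, two, and three years". On the error term it says: "These comparisons will be made using the common estimate of error obtained from a three group x three time point repeated measures" analysis of covariance, "with the baseline spherical equivalent used as a covariate".

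The effect sizes and the SD that follow are three-year figures. In the source study, "myopia progression was $-1.29 \text{ D} \pm 0.71$ over three years". The 50% scenario means "reducing the amount of myopia progression by roughly 0.65 D in the +2.50 D add group", with the middle arm "reducing myopia progression by 0.30 D in the second add".

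The manual has no statistical analysis chapter. It states no covariance structure, no sphericity check or correction, and no year-specific variance. It does not say whether the primary contrast is at three years, at each year, or averaged over years. Table 8-2 names cycloplegic autorefraction as the primary outcome without a time point. Chapter 31 (Publications) leaves a detailed analysis plan to be developed with the coordinating center for each approved paper.

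**The concern.** After adjustment for baseline refraction, the residual at each annual visit is essentially the child's cumulative progression plus measurement error. Progression is zero at baseline by definition and has an SD of 0.71 D at three years. If children progress at different rates, the residual spread is smaller at Year 1 than at Year 3. A single error estimate pooled over the three visits is then too large for Year 1 and too small for Year 3. A sphericity correction of the overall F-test does not repair contrasts at a single year.

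At stake is the three-year arm difference, the time point for which the Aim 1 effect sizes are stated. Its p-value would be too small and its confidence interval too narrow.

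**Working it through.** **Inputs from Chapter 5.** Alpha 0.05; three-year SD 0.71 D; differences between the +2.50 D add and single vision of 0.65, 0.50 and 0.40 D; 98 per arm, or about 88 after 10% loss (98 × 0.9 = 88.2). The SDs at Years 1 and 2 are not given and are assumed below.

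**The plan's own figures.** A three-group one-way F-test (noncentral F) with SD 0.71, alpha 0.05, power 80% and arm effects 0 / 0.30 / 0.65, 0 / 0.25 / 0.50 and 0 / 0.20 / 0.40 D gives 24, 40 and 62 per group. This matches the manual exactly; for the first scenario, "then the sample size required at 80% power is 24 per treatment group". The manual's sentence on error rates also gives a beta of 0.10, but 90% power would need 32, 53 and 81. These sample sizes use the three-year SD directly, so pooling over years does not touch them.

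**Effect of pooling on a three-year contrast.**
- Pooled variance = mean of the three yearly variances.
- Ratio r = sqrt(pooled variance / Year 3 variance).
- Actual two-sided level at Year 3 = 2 × (1 − Phi(1.96 × r)).
- Correct SE of a pairwise three-year difference, 98 per arm = 0.71 × sqrt(2/98) = 0.101 D. The pooled SE is r times this.

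| Assumed pattern | SDs, Years 1/2/3 (D) | Pooled SD (D) | r | Pooled SE (D) | SE too small by | Level at Year 3 | Level at Year 1 |
|---|---|---|---|---|---|---|---|
| Constant SD | 0.71/0.71/0.71 | 0.71 | 1.00 | 0.101 | 0% | 5% | 5% |
| Slow growth (SD as fourth root of time) | 0.54/0.64/0.71 | 0.63 | 0.89 | 0.091 | 11% | 8% | 2% |
| Variance proportional to time | 0.41/0.58/0.71 | 0.58 | 0.82 | 0.083 | 18% | 11% | 0.6% |
| SD proportional to time | 0.24/0.47/0.71 | 0.51 | 0.72 | 0.073 | 28% | 16% | below 0.1% |

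Worked line, variance proportional to time: r = sqrt((1/3 + 2/3 + 1)/3) = sqrt(2/3) = 0.816; 1.96 × 0.816 = 1.60; level 0.11. For SD proportional to time: r = sqrt((1/9 + 4/9 + 1)/3) = sqrt(14/27) = 0.72; level 0.158, so a nominal 95% interval covers about 84%.

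**Simulation check.** Baseline-adjusted ANCOVA, 98 per arm, 4,000 runs, no true arm difference, +2.50 D add versus single vision:

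- Year 3 with pooled error: 0.118 (variance proportional to time), 0.151 (SD proportional to time), 0.127 (SD growth plus an assumed 0.20 D measurement error), 0.051 (constant variance).
- Year 3 with its own error: 0.048 to 0.054.
- Contrast averaged over the three years, with its own between-child error: 0.048 to 0.056 in every case.

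**Power with the correct three-year SE.** For 0.40 D: 97.6% at 98 per arm and 96.2% at 88 per arm.

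**The case against.** The strongest reply is that the faulty analysis is inferred. The sentence speaks of the mean spherical equivalent over the three visits. The error could be common to the three arms rather than to the three years, or it could be the between-child error for an arm effect averaged over visits. On that averaged reading the test is valid in every scenario above. A repeated measures ANCOVA does not by name impose equal variances, and model detail may come in the later per-paper plan. The size of any error also rests on Year 1 and Year 2 SDs that the manual does not give.

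Most of this stands, and it makes the point conditional. It does not dispose of it. The natural reading of one common error taken from the whole three-by-three model is an error pooled over years, and nothing elsewhere in the manual corrects for that. If the averaged contrast is meant, it is not the quantity on which the Aim 1 figures are built: were the effect to accrue evenly, the average would be (1/3 + 2/3 + 1)/3 = two-thirds of the three-year effect. Either way the text needs to say which contrast is meant.

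Three stronger readings are tempting, and the documents do not support them.

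- **The three-year test is certainly liberal.** One SD at one time point cannot show growth between Years 1 and 3. Growth is plausible, but it is an assumption.
- **The trial's size is compromised.** The Aim 1 figures of 24, 40 and 62 reproduce with the three-year SD. The total of 294 comes from Aim 3 (267, adjusted for loss); Aim 1 needs at most 186.
- **Real Year 1 differences would be hidden.** The Year 1 test would be conservative if the spread grows. But a 50% effect accruing evenly (0.65/3 = 0.217 D) would still be detected with about 82% power under variance proportional to time: critical difference 1.96 × 0.083 = 0.162 D, true SE 0.41 × sqrt(2/98) = 0.059 D.

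**Conclusion.** The point holds conditionally. If the common error is pooled over years and applied to a three-year arm contrast, and if the spread of cumulative progression grows with time, the three-year standard error is too small. The understatement is 11% to 28% under the growth patterns tried and nil with a constant SD. The nominal 5% test then runs at about 8% to 16%, against 5% with no growth. The yearly SDs are assumptions throughout, apart from 0.71 D at Year 3.

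This is more than a missing detail, because the manual states an error term and a better one is available at almost no cost. It is not a demonstrated error, because the text does not settle which contrast is tested.

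**What to change.** In Chapter 5, Specific Aim 1, and in the analysis plan for the primary paper:

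- Replace the common error with an arm-by-year repeated measures model that has an unstructured within-child covariance and baseline-by-year terms.
- Name the three-year contrast as primary, or state that the contrast averaged over the three years is.
- Take each year's arm contrasts and confidence intervals from that year's own variance.

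The cost is a wording change and a few extra covariance parameters, estimated from roughly 265 children (294 × 0.9). The three-year interval may be wider than under pooling. No change in sample size follows.

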Analysis of the relationship between the amount of peripheral defocus and the amount of myopia progression will provide information on how the level of peripheral defocus may affect the progression of myopia. That is, are higher levels of peripheral myopic defocus associated with a decreased rate of foveal myopia progression? Peripheral defocus is measured in this study at multiple locations (20°, 30°, and 40°) in two gaze positions (nasal and temporal). The association between peripheral defocus and myopia progression will be assessed using a correlation analysis and linear regression. Based on recent work by Sankaridurg et al. (2011), a clinically meaningful magnitude of correlation between peripheral defocus and myopia progression is 0.25. To detect a correlation as small as 0.25 at 80% power would require 123 subjects total.

Specific Aim 3: to determine whether changes in ocular shape differ between children wearing single vision and soft bifocal contact lenses to test the hypothesis that peripheral myopic defocus globally slows eye growth

Aim 3 is designed to evaluate differences in the change in ocular shape between the two soft bifocal and single vision contact lens groups using the measure of relative peripheral refractive error across the horizontal and vertical meridians of the eye. Relative peripheral refractive error is computed by subtracting the central cycloplegic spherical equivalent autorefraction from the peripheral spherical equivalent autorefraction, each measured with no refractive

error correction. Analyses will use a repeated measures ANCOVA with gaze direction and fixation as within-subject factors. To increase the efficiency of the F-tests performed as part of the ANCOVA, the total sample size will be equally allocated between the soft bifocal and single vision contact lens groups.

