Sample size estimates are based upon a magnitude difference of the change in “ocular shape” between the single vision contact lens and the +2.50 D add bifocal treatment groups of 0.40 D. In order to ensure that we have adequate sample size to find a true difference, we have made the assumption that the +1.50 D add bifocal group will experience a change that is intermediate between the other two groups (i.e., 0.20 D). Making this assumption gives us a conservative estimate of sample size (i.e., the maximum sample size). While no longitudinal data assessing the amount of change in periphery that can be considered clinically meaningful, it is reasonable to assume that a clinically meaningful change in the center would be considered a clinically meaningful change in the periphery as well. As such, we know that the minimal difference in central refractive error change that has been detected in previous studies is 0.13 D over one year. If this amount of difference in refractive error change continues for three years, then the minimal meaningful difference would be 0.39 D, which we rounded to a 0.40 D difference. The standard deviation arises from the Study of Theories about Myopia Progression, and is set at 0.85, which represents the most conservative standard deviation in the change in relative peripheral refraction seen across measures. Using this information the sample size required to detect this magnitude of difference in the change in ocular shape between treatment groups with 80% power is 89 subjects per group, for a total sample size of 267 subjects.

Sample Size Conclusion

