Table 5-1 provides a summary of the sample size requirements based on the three study aims. Although we strive to retain all subjects, the sample size will be adjusted to account for a possible 10% loss to follow-up. This is a reasonable expectation. [name], when at Ohio State, had a retention rate of 98% in his Study of Theories about Myopia Progression clinical trial, and other clinical vision studies conducted at the University of Houston have retention rates exceeding 90%. Likewise, [name] experiences at Ohio State with ACHIEVE (OSU clinic saw 100% of subjects for final visit) and the Contact Lens and Myopia Progression trial (100% of subjects at final visit) indicate that a 10% loss to follow-up is an acceptable assumption. Using the maximum sample size from Table 5-1 (n=267) and adjusting for 10% loss to follow-up gives a **total sample required of 294** (98 children assigned to each treatment group).

Table 5-1: Total sample size required at 80% power in the Soft Bifocal Contact Lens Myopia Control Study

| Aim | Total sample |
|----------------------|--------------|
| Specific Aim 1 | |
| 50% treatment effect | 72 |
| 40% treatment effect | 120 |
| 30% treatment effect | 186 |
| Specific Aim 2 | 123 |
| Specific Aim 3 | 267 |

Chapter 6: Timeline

During the first six months of funding, preparation for the trial will begin. The DSMC will meet as early as possible (after preparation of study forms and DSMC binders) in order to finalize the protocol. Once the protocol is finalized, certification of examiners will begin at the FIG meeting, both near the end of the initial six-month period.

Recruitment will begin at the beginning of month seven and continue for 15 months. All follow-up visits will begin within one week of the first subject visit. The last one-year, two-year, and three-year visits are expected to be complete within one month of the anniversary date of the last subject enrolled.

The DSMC will meet annually, after recruitment and each year of follow-up is complete and the data are analyzed. FIG meetings will be held after each DSMC meeting in order to update protocols, motivate investigators, and discuss problems encountered. Writing groups will also meet during the FIG meetings.

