Subjects who meet the entry criteria will be randomly assigned to single vision, soft bifocal with +1.50 D add, or soft bifocal with +2.50 D add contact lenses for at least three years. The randomization assignment will be conducted through REDCap, the web-based, electronic data capture system that also verifies the eligibility of the subject. The randomization assignment will be stratified by clinical site and age, using a random permuted block design to ensure sequential balance of the distribution of the three treatments among the age groups and clinic sites. A child is considered enrolled once the randomization assignment and study identification number are received. When the randomization assignment is received from the web site, the investigator should complete the Randomization Form. The Randomization Form should not be sent to the Data Coordinating Center, it should be maintained in the subject's study binder.

Chapter 12: Masking

This will be a double-masked study. Subjects will not know the contact lens modality to which they are allocated. Contact lens boxes will be eliminated, and all contact lens brandings will be de-identified prior to dispensing. At no point during the study will the subjects be told their treatment assignment. There are no identifying marks on the contact lenses that would help subjects identify their treatment. All contact lens care will be similar, regardless of contact lens modality.

Masked examiners will perform masked measurements at the baseline and annual visits. The masked examiners will not be allowed in the clinical area, other than to perform their masked examination duties. The masked examiners will never examine the subjects while they are wearing contact lenses. All contact lens cases, packages, and solutions will be placed in a hidden location during the masked portion of the examinations, and subjects will be told not to discuss their contact lens wear or care with the masked examiner.

Four outcomes will be conducted by an examiner who is masked to the assigned treatment group.

- Cycloplegic autorefractometry (OU)
- Axial length (OU)
- Peripheral refractive error without a contact lens (OD)
- Peripheral eye length (OD)

Assessment of Masking

We will monitor both subject and masked examiner masking at each annual examination by asking the following questions:

1. How sure are you of whether you are / the subject is wearing bifocal or non-bifocal contact lenses?
 - a. Very sure
 - b. Sure
 - c. Unsure

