The investigator should submit an abstract and a short description of the proposed paper including co-authors, data to be reported and timeline for drafts and submission. This information should be sent to the Study Chair. The Executive Committee is responsible for reviewing the proposal's merit and deciding if it should be a study publication. This review process is intended to ensure the quality of study publications and to refine the proposal. The Executive Committee is responsible for determining priorities (timeline and order of preparation) of proposed papers/presentations. Upon approval of the proposed paper/presentations, a detailed analysis plan and timetable are developed with the DCC.

The DCC is responsible for maintaining a database that tracks proposed and approved study publications and presentations. A list of approved study publications and presentations will be distributed to all investigators on a regular basis. Interested investigators are invited to contact the primary author to add their name to the writing group.

Should the workload associated with the preparation of papers exceed the resources of the DCC, it will be the responsibility of the DCC in conjunction with the Executive Committee to establish priorities. It will be the responsibility of the DCC to contact primary authors when timelines are not met. Major problems in the preparation of manuscripts are referred to the Executive Committee.

The primary author is responsible for coordinating all activities related to the writing and submission of papers and abstracts. This includes arranging conference calls, discussing analytic plans with the DCC, assigning writing responsibilities to co-authors, maintaining timeliness, determining the order of authorship, circulating drafts to co-authors, and circulating final drafts to the Executive Committee. Upon circulation of the draft, there will be a two-week period during which members can make comments about the paper.

If the focus of the paper changes as it moves from abstract to the manuscript stage, the primary author will notify the Study Chair in writing. The Study Chair will be responsible for insuring that the revised proposal receives appropriate review.

Each publication must acknowledge support as follows: "NIH U10 EY023204, 023206, 023208, 023210, P30 EY007551, and UL1 TR001070."

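### Randomisation is stratified by site and age, but neither the stated Aim 1 model nor the stated Aim 3 model names them; adding them is free and gains a little power if they are prognostic

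*Combined protocol and SAP*

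**What the plan says.** - **Chapter 11 (Randomization):** "The randomization assignment will be stratified by clinical site and age, using a random permuted block design". The age bands and the block size are not given there.
- **Chapter 5, Specific Aim 1:** a three-group by three-time-point repeated measures ANCOVA, "with the baseline spherical equivalent used as a covariate". No other covariate is named.
- **Chapter 5, Specific Aim 3:** "Analyses will use a repeated measures ANCOVA with gaze direction and fixation as within-subject factors". It is called an ANCOVA, but no between-subject covariate is named, so the list is evidently incomplete.
- **Chapter 31, Publications:** "Upon approval of the proposed paper/presentations, a detailed analysis plan and timetable are developed with the DCC". This defers detail to the paper stage and does not mention the strata.

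Nothing else in the supplied text adds site or age to either model, and nothing states how strongly they predict the outcomes.

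**The concern.** Blocking within site and age removes the variation due to those factors from the treatment comparison. A model without them still counts that variation as residual error. The estimated standard error is then larger than the true one, and the F test rejects less often than its nominal 5%. The trial would have paid for balance at randomisation and not used it in the analysis.

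Only efficiency is at stake. The omission cannot produce a false claim for treatment, and if neither factor is prognostic nothing is lost. Aim 3 has more to gain, because it sets the trial size and is planned at 80% power.

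**Working it through.** **Inputs from Chapter 5.** Alpha 0.05; power 80% (the text also prints β = 0.10, but only 80% reproduces the stated sizes). Group means 0 / 0.20 / 0.40 D, for the 30% effect in Aim 1 and for Aim 3. SD 0.71 D (Aim 1) and 0.85 D (Aim 3). 98 per group less 10% = 88.2, taken as 88.

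**Assumed.** R², the share of outcome variance explained by site and age (for Aim 1, of the variance left after baseline refraction); two sites by two age bands, which adds 3 model degrees of freedom.

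**Reproducing the plan.** Three-group F test with noncentrality λ = n × Σ(μᵢ − μ̄)² / SD² = n × 0.08 / SD².
- Aim 1: 62 × 0.08 / 0.5041 = 9.84, power 80.2%. The plan "yields a sample size of 62 subjects per treatment group".
- Aim 3: 89 × 0.08 / 0.7225 = 9.85, power 80.5%. The plan states 89 per group.

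**Power at 88 per group.** With R² = 0, λ is 88 × 0.08 / 0.5041 = 13.97 (Aim 1) and 88 × 0.08 / 0.7225 = 9.74 (Aim 3). Under stratified blocking the true noncentrality is λ / (1 − R²) whether or not the model contains the strata.
- Strata included: usual critical value on 258 error df.
- Strata omitted: the error mean square is inflated by 1 / (1 − R²), so the effective critical value is 3.03 / (1 − R²) on 261 df. The standard error is too wide by 1/√(1 − R²) − 1.

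To put R² in dioptres: two equal strata that differ by d give R² = d² / (4 SD²), so d = 2 × SD × √R².

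| R² | d, Aim 1 / Aim 3 (D) | Aim 1 power, omitted v included | Aim 3 power, omitted v included | SE too wide by | Actual level of 5% test, strata omitted |
|---|---|---|---|---|---|
| 0 | 0 / 0 | 92.4 v 92.4% | 80.0 v 80.0% | 0% | 5.0% |
| 0.02 | 0.20 / 0.24 | 92.6 v 93.0% | 80.1 v 80.8% | 1.0% | 4.7% |
| 0.05 | 0.32 / 0.38 | 92.8 v 93.7% | 80.3 v 82.1% | 2.6% | 4.3% |
| 0.10 | 0.45 / 0.54 | 93.3 v 94.9% | 80.7 v 84.2% | 5.4% | 3.6% |
| 0.20 | 0.64 / 0.76 | 94.1 v 96.9% | 81.5 v 88.4% | 11.8% | 2.4% |

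**Benchmark.** For Aim 3 the plan takes 0.13 D a year over three years, "then the minimal meaningful difference would be 0.39 D, which we rounded to a 0.40 D difference". If two equal strata differed by that same 0.40 D:
- Aim 1: R² = 0.16 / (4 × 0.5041) = 0.079; power 93.1 v 94.4%, a gain of 1.3 points.
- Aim 3: R² = 0.16 / (4 × 0.7225) = 0.055; power 80.4 v 82.3%, a gain of 2.0 points before rounding.

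**Simulation check.** 20,000 trials per setting, 88 per arm, balanced within 2 × 2 strata. At R² = 0.20, Aim 1 power was 94.2 v 96.8% and Aim 3 power 81.6 v 88.6%. With no treatment effect, the test without strata rejected in 4.3%, 3.6% and 2.4% of trials at R² 0.05, 0.10 and 0.20; the test with strata stayed at about 5%.

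**Cost if the strata are not prognostic.** With 9 extra degrees of freedom (2 sites × 5 single-year ages) and R² = 0, Aim 3 power goes from 79.99% to 79.97% and Aim 1 power from 92.45% to 92.44%.

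**The case against.** The strongest reply is that Chapter 5 explains how the sample size was obtained and is not a full analysis plan. Silence there is not a decision to leave the strata out, least of all for Aim 3, whose covariate list is plainly incomplete. That stands as a limit on wording: the strata are not stated, and nobody has said they will be excluded. But these are the only models the supplied text describes, and the later plan promised in Chapter 31 does not commit to the strata.

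The gain may also be negligible. No R² is given, and the upper ends of the ranges need strata that differ by 0.64 to 0.76 D, well above the plan's 0.40 D target. Aim 1 already has 92.4% power at its smallest planned effect. The Aim 3 SD is one "which represents the most conservative standard deviation in the change in relative peripheral refraction seen across measures"; at SD 0.80 or 0.75, power without strata is 84.8% or 89.3%. All of this stands, and it makes the point a small one.

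The figures are one-way approximations to repeated measures analyses. Group-by-time tests gain only if the strata predict the pattern over time, and baseline refraction may already absorb part of any age effect in Aim 1. This also stands.

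Finally, the manual is version 1.8 of May 2018, and Chapter 6 says "The DSMC will meet annually, after recruitment and each year of follow-up is complete and the data are analyzed", so some outcome data may already have been analysed. That weakens any claim of full pre-specification. It does not remove the remedy: Table 6-2 expects the last subject to complete in August 2018, so the model could still be fixed before the final treatment comparison.

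**Conclusion.** The point holds. The randomisation uses site and age, and the stated Aim 1 and Aim 3 models do not name them. If they are prognostic, the tests are conservative: 0 to about 3 power points lost for Aim 1 and 0 to about 7 for Aim 3 over R² from 0 to 0.20, with gains nearer 1 to 2 points at the 0.40 D benchmark. For R² up to 0.10 the conservatism is mild; at 0.20 the actual level is about half the nominal one. No conclusion of the trial is threatened.

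These sizes rest on the assumed R², two age bands, 88 completers per group with dropout at random, balance within strata, and a single between-group comparison in place of the repeated measures model. The direction of the effect does not depend on the value of R², provided it is above zero.

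**What to change.** Add one line to the analysis plan: site and the age stratum used at randomisation enter the Aim 1 and Aim 3 models as fixed effects, alongside the baseline value of the outcome. State the age bands.

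Date the change and make it before the final treatment comparison is seen. Chapter 6 has data analysed for the DSMC each year and the primary paper drafted once 75% of subjects have completed, so a plan written only at the paper stage could follow sight of outcome data. Record what had already been analysed when the line was added.

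Both variables are already held for randomisation. Sample size, visits and data collection do not change.
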